4 STUDY DESIGN

4.1 OVERALL DESIGN

Hypotheses for this trial include:

- 1) Patients who stop adalimumab will have a shorter time to uveitis recurrence compared to those who continue treatment. Patients randomized to continue treatment will have a higher rate of adverse events compared to patients randomized to stop treatment.
- 2) Patients with higher serum levels of MRP8/14, higher ESR, higher ADA, and higher CRP will have a higher uveitis recurrence rate compared to patients with lower serum levels. In addition, period of inactive uveitis, age at randomization, and duration of adalimumab treatment before randomization will be associated with uveitis recurrence rate.
- 3) A smaller proportion of patients who stop adalimumab will have controlled ocular inflammation at Month 6 and Month 12 compared with patients who never stop adalimumab. In addition, among patients who stop adalimumab and have a uveitis recurrence, anti-adalimumab antibodies will be associated with a longer time to regaining uveitis control after restarting treatment. MRP8/14 levels will be associated with the likelihood of establishing control of ocular inflammation after restarting adalimumab treatment following uveitis recurrence.

This study is a phase IV clinical trial.

The study design is a multicenter, randomized, placebo-controlled, superiority trial comparing stopping adalimumab treatment to continuing adalimumab treatment for patients with JIA-associated uveitis or CAU who have achieved corticosteroid-sparing control of inflammation on 12 consecutive months of adalimumab or a biosimilar treatment. Patients randomized to continue adalimumab treatment will receive the standard clinical practice weight-based dose of adalimumab. Patients in both arms will remain on their current dose of concomitant antimetabolite therapy if applicable. Further detail on dosing and administration of study treatment is provided in **Section 6.1.2**.

Randomization will be stratified by use of concomitant antimetabolite therapy and by country. Patients will be treated as originally randomized until treatment failure is declared, at which point, they may be treated per best medical judgement. The primary outcome will be time to treatment failure (as defined in **Section 3** primary endpoint) up to 12 months post-randomization. Rates of disease recurrence and rates of adverse events will also be compared between the two treatment groups. All patients will be followed through Month 12 for the purpose of obtaining secondary, long-term clinical outcome data.

Patients originally randomized to stop adalimumab treatment who experience a treatment failure may restart adalimumab treatment during the trial and will be assessed at Month 12. Primary outcome analysis will be intent-to-treat, but a secondary per-protocol analysis will be performed, and subgroup analyses will be performed on patients who stop and restart adalimumab treatment. Further detail on statistical analysis is provided in **Section 9.4**.

MRP8/14 serum levels, ESR, CRP, and adalimumab antibody levels will also be measured periodically during the trial. These biomarkers will be assessed as potential predictors for disease recurrence in patients with JIA-associated uveitis or CAU.

The trial will have 10 enrollment centers in the U.S., 9 in the UK, and 1 in Australia. Additional sites may be added during the study to facilitate enrollment. U.S. study sites will include the F.I. Proctor

Foundation at University of California San Francisco (UCSF), Children's Hospital of Philadelphia, Cincinnati Children's Hospital, Children's Mercy Hospital in Kansas City, MO, University of Utah Health in Salt Lake City, Colorado Retina Associates in Lakewood, CO, University of California Davis Eye Center in Sacramento, CA, Vanderbilt Eye Institute in Nashville, TN, University of Texas in Austin, TX, and University of Miami, FL. UK study sites will include Great Ormond Street Hospital in London, University Hospitals Bristol, Alder Hey Children's Hospital in Liverpool, Great North Children's Hospital in Newcastle, Sheffield Children's Hospital, Cambridge University Hospital, Royal Manchester Children's Hospital, University Hospital of Leicester, and Norfolk and Norwich University Hospital. The Australian study site is The Royal Children's Hospital in Melbourne.

4.2 SCIENTIFIC RATIONALE FOR STUDY DESIGN

Justification for placebo treatment: As both patients and those assessing outcomes could introduce bias, complete masking of the treatment is ideal for this study. This concern is especially pertinent for the pediatric population, since it is difficult to prevent young patients from discussing their treatment with their physician. Our primary outcome is time to treatment failure, where treatment failure is defined as a recurrence of ocular inflammation (≥ 2 -step increase in AC cell observed at 2 consecutive visits at least 7 days apart; $>0.5+$ AC cell for ≥ 28 days; $\geq 3+$ AC cell observed at a single visit; or $>0.5+$ vitreous haze, active retinal/choroidal lesions, or macular edema at a single visit) and/or a recurrence of joint inflammation that is persistent and severe enough to necessitate unmasking to manage the arthritis recurrence. While an attempt will be made to ensure the grading of ocular inflammation is as standardized as possible, complete removal of subjectivity in inflammation grading is impossible. Furthermore, we plan to assess adverse events and quality of life as secondary outcomes, which rely on patient self-report. Given that self-report is involved in both the primary and secondary outcome assessments, masking of subjects is also necessary to remove any potential bias in assessing the outcomes for our study.

Justification for superiority: There is clinical utility in determining if one treatment plan is more effective for reducing the risk of recurrence of ocular inflammation. The findings of this trial could provide justification for either stopping adalimumab or continuing adalimumab for long-term management of JIA-associated uveitis and CAU, which are chronic conditions. Therefore, a superiority trial design is warranted.

Potential problems with placebo treatment: We hypothesize that stopping adalimumab will result in a shorter time to treatment failure and higher uveitis recurrence rates compared to continuing adalimumab. In anticipation of this possibility, we have allowed for patients to restart adalimumab or be treated per best medical judgement for the remainder of the study period. The primary analysis will be intent-to-treat, but we will also collect clinical outcome data at Month 12 to assess whether the initial strategy of stopping treatment results in worse outcomes compared to the initial strategy of continuing therapy.

4.3 JUSTIFICATION FOR DOSE

Patients randomized to continue adalimumab will receive the standard clinical practice weight-based dose of adalimumab. The standard clinical practice is self-administration of adalimumab subcutaneously at a dose of 40mg every other week for patients ≥ 30 kg and 20mg every other week for patients < 30 kg. Patients randomized to stop adalimumab will receive placebo treatment. The volume-matched placebo will be administered subcutaneously for masking purposes every other week.

Patients must be on a stable dose of adalimumab or a biosimilar of adalimumab for a minimum of 180 days prior to randomization at a maximum dose of 40mg every other week. Patients receiving treatment on a weekly basis will not be eligible for the study. Treatment must be decreased to every other week and remain stable for at least 180 days in order to gain eligibility. We expect most patients will be on the appropriate weight-dependent dose of adalimumab. In the event that a patient is on a higher dose than appropriate for their weight (i.e. 40mg biweekly if <30kg), this dose must be tapered to 20mg biweekly and must be stable for at least 180 days prior to enrollment. In the event that a patient is on a lower dose than appropriate for their weight (i.e. 20mg biweekly if ≥30kg), they may enroll in the trial as long as the dose has been stable for at least 180 days and uveitis and arthritis have been inactive (per definitions above) for at least 12 months, and if randomized to continue adalimumab they will receive the standard weight-based dose. During the course of the study, any patient receiving the lower adalimumab dose (20mg biweekly) who reaches the weight of ≥30kg for at least 2 consecutive visits (≥28 days apart) will be switched to the 40mg biweekly dose strength on their second visit. These requirements will ensure that all patients in the trial receive comparable doses of study treatment and have not had any recent changes to treatment that would affect their outcomes during the trial.

If on a concomitant antimetabolite, patients will continue their same dose and route of administration regardless of treatment arm. We anticipate the dose of methotrexate may range from 10 to 20 mg/m² with a maximum dosage of 25 mg per week according to standard clinical practice for methotrexate treatment in the setting of JIA.⁵⁹ Patients treated with >25 mg/week will not be eligible for the trial. Such patients must decrease the dose to ≤25 mg/week and must be on a stable dose and the same route of administration for ≥90 days prior to enrollment. Similarly, the maximum allowable dose of mycophenolate mofetil is 3 g daily, azathioprine is 250 mg/day, and leflunomide is 20 mg/day and the dose and route of administration must be stable for ≥90 days prior to enrollment. This restriction will limit potential bias from a recent change in concomitant immunomodulatory treatment dose and its therapeutic effects prior to entering the trial. Note, patients should not be on any other immunosuppressive agent.

If on topical corticosteroids, the dose must be ≤2 drops per day of 0.1% prednisolone acetate or equivalent, and dose must be stable for ≥90 days prior to enrollment. This requirement will ensure that all patients in the trial receive comparable doses of topical corticosteroids, a standard first-line treatment for anterior uveitis. In addition, this restriction will limit potential bias from any recent changes to treatment that would affect patient's clinic outcomes during the trial.

4.4 END OF STUDY DEFINITION

Participants are considered to have completed the study when they complete the Month 12 visit or the last scheduled procedure for the Month 12 visit as shown in the Schedule of Activities (SoA), **Section 1.3**. The end of the study is defined as completion of the last patient's visit or procedure shown in the SoA. Note that if inflammation is increased at Month 12 to a treatment failure criterion threshold, a follow-up visit must be conducted to determine whether the treatment failure criteria are met or not. If treatment failure is declared with fewer than 90 days remaining in follow-up, patients will be followed beyond Month 12 so that all patients have a minimum 90 days of follow-up after treatment failure. There will be a 90-day post-treatment failure study visit where the Clinical Eye Exam, Visual Acuity, OCT, and Adverse Event Report will need to be completed in addition to the Month 12 study visit. Standard of care labs will also be drawn only if the patient is on an antimetabolite and if more than 90 days have passed since their last standard of care lab draw. Follow-up could be extended up to 15 months if there is late treatment failure.

5 STUDY POPULATION

5.1 INCLUSION CRITERIA

To be eligible to participate in this study, an individual must meet all of the following criteria:

- Stated willingness to comply with all study procedures and availability for the duration of the study period
- History of JIA or CAU, diagnosed prior to 16 years of age (patient may be older than 16 at time of enrollment)^a
- ≥ 2 years of age (per FDA approval for use in children with polyarticular JIA) ^b
- Formal diagnosis of JIA-associated uveitis^c or CAU^d with no other suspected etiology
- ≥ 12 consecutive months of controlled ocular inflammation ($\leq 0.5+$ anterior chamber cell, $\leq 0.5+$ vitreous haze, and no active retinal/choroidal lesions in either eye)
- ≥ 12 consecutive months of controlled arthritis verified by a pediatric rheumatologist (see **MOP Section 3.3.1** for definition of controlled arthritis) if defined as JIA-associated uveitis
- ≥ 12 consecutive months of treatment with adalimumab^e and/or a biosimilar of adalimumab^f
- ≥ 180 days on a stable dose of adalimumab or a biosimilar of adalimumab; must be biweekly dose of no greater than 20mg (if < 30 kg) or 40mg (if ≥ 30 kg)
- If on a biosimilar of adalimumab, ≥ 90 days on the biosimilar
- If on concomitant antimetabolite (injectable or oral methotrexate, mycophenolate mofetil, azathioprine, or leflunomide), dose must be ≤ 25 mg weekly for methotrexate, ≤ 3 g daily for mycophenolate mofetil, ≤ 250 mg daily for azathioprine, or ≤ 20 mg daily for leflunomide; dose and route of administration must be stable for ≥ 90 days
- If on topical corticosteroids, dose must be ≤ 2 drops prednisolone acetate 1% or equivalent per day and stable for ≥ 90 days
- Willingness to limit consumption of alcohol during the study period
- Agreement to avoid live attenuated vaccinations
- Agreement to use highly effective contraception^g for ≥ 28 days prior to screening and throughout study period (for males and females of reproductive age)
- Suitable, in the opinion of the Investigator, to continue treatment with adalimumab or placebo per regional labeling
- No contraindications to receive adalimumab as per the local Summary of Product Characteristics (SmPC)

There are no gender, race, or ethnicity restrictions for this study.

^aPatients can be older than 16 years of age at enrollment, but original diagnosis of arthritis must have been made prior to age 16 per the clinical definition of JIA

^bAdalimumab is FDA approved for use in children ≥ 2 years of age

^cBy history, chronic or recurrent, relatively asymptomatic (not limiting daily activities or requiring analgesics) unilateral or bilateral anterior uveitis characterized by no or minimal conjunctival injection (no ciliary flush)

^dIf no history of JIA, must have a relatively asymptomatic (not limiting daily activities or requiring analgesics) unilateral or bilateral anterior uveitis characterized by no or minimal conjunctival injection (no ciliary flush)

^e ≤ 2 weeks of interruption in treatment is allowed (e.g., due to surgery, infection) provided uveitis and arthritis inflammation remains controlled

^fUK patients on a biosimilar of adalimumab are eligible

^gEffective contraception includes pharmacologics, devices, and barrier methods

5.2 EXCLUSION CRITERIA

Any one of these excludes the patient:

- Intraocular surgery in the past 90 days or planned surgery in the next 12 months
- Severe cataract or opacity preventing view to the posterior pole in both eyes
- Chronic hypotony (<5mmHg for ≥90 days) in either eye
- Treatment with oral corticosteroids^a or intraocular corticosteroid injection within the last 12 months
- Use of NSAID eye drops within the last 90 days
- Acute anterior uveitis characterized by redness and symptoms, including but not limited to floaters, pain, and light sensitivity
- Pregnancy or lactation (a pregnancy test will be conducted at baseline and all follow-up visits for females of reproductive age)
- Presence of intraretinal or subretinal fluid in either eye
- Prior safety or tolerability issues with adalimumab
- History of cancer, active tuberculosis, or hepatitis B
- Other medical condition expected to dictate treatment course during the study
- Any of the following laboratory test results on their most recent tests within the past 90 days prior to screening/enrollment^b: leukocyte count <2500, platelet count ≤75000, hemoglobin<9.0, AST or ALT ≥ 2 times the upper limit of normal range, creatinine ≥1.5

Note that patients with acute anterior uveitis, which is often associated with enthesitis-related arthritis including the HLA-B27 positive subtype, are not eligible. Beyond the tests listed above, the remainder of the work-up is at the discretion of the investigator and should be tailored to the clinical situation. Distinguishing between infectious and non-infectious uveitis is part of standard of care and should be dictated by the patient's clinical exam. A prior attempt at discontinuing adalimumab or other TNF-alpha inhibitor is not an exclusion criterion.

5.3 LIFESTYLE CONSIDERATIONS

During this study, participants must:

- Limit consumption of alcohol during the study period
- Avoid live attenuated vaccinations
- Use highly effective contraception for at least 1 month prior to screening, throughout study period, and at least 5 months following the trial (for males and females of reproductive potential)

^a Oral corticosteroids are permitted if prescribed for conditions unrelated to JIA/CAU (e.g., allergic reaction, asthma) and if not anticipated to need again during the study.

^b Normal lab readings are required to have been from within 90 days prior to an enrollment if the patient is on an antimetabolite, and can be from within 180 days prior to enrollment if not on an antimetabolite. If there are abnormal labs from within 90/180 days, but their most recent labs are normal, proceed to enroll.

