^fAdverse Event (AE) check phone call: Patients are contacted approximately 70 days after their last study visit. Only the AE form is completed.

^gPatients randomized to continue adalimumab and patients randomized to stop adalimumab who have a treatment failure and restart will be provided open-label drug until Month 12 (or Month 15 if treatment failure occurs at Month 12).

Form Completion Schedule

After completing each study visit, study coordinators will review the electronic case report forms for completion and accuracy and submit them electronically via REDCap. If study visit data are recorded on hard copies of the forms, these paper copies should be scanned and emailed to the Coordinating Center ([contact]) and kept in a secure location at the site. All US centers are part of the Childhood Arthritis and Rheumatology Research Alliance (CARRA) and submit data to the registry for their JIA patients. As we are collecting similar data on an overlapping patient population, CARRA has allowed us to use their data collection forms. We will collect data using forms developed specifically for ADJUST in addition to several forms from the CARRA registry that are applicable to the study procedures and data collected for this study.

	Baseline	Months 1-4	Month 6	Months 8 & 10	Month 12	Treatment Failure ^a	Additional Visit ^b
Patient Consent Forms	✓						
Eligibility and Screening Form	✓						
Baseline Treatment Assessment Form	✓						
Baseline Demographics Form	✓						
Baseline Ophthalmology Form	✓						
Baseline Rheumatology Form	✓						
Clinical Eye Exam Form	✓	✓	✓	✓	✓	✓	✓
Arthritis Evaluation Form	✓	Month 3	✓		✓	✓	
Visual Acuity Form	✓	✓	✓	✓	✓	✓	✓
OCT Form	✓	✓	✓	✓	✓	✓	✓
Standard of Care Lab Form	✓	Month 3 ^c	✓	Month 8 or 10 ^c	✓	✓	✓ ^b
Research Sample Lab Form	✓		✓		✓	✓	
Adverse Event Checklist	✓	✓	✓	✓	✓	✓	✓ ^d
Quality-of-Life Questionnaires (CHAQ, CVFQ, EYE-Q, EQ-5D-Y)	✓		✓		✓	✓	
Treatment Assessment Form ^e	✓	✓	✓	✓	✓	✓	✓
Medication Adherence Log	✓	✓	✓	✓	✓	✓	✓
Patient Dropout Form (if applicable)		(✓)	(✓)	(✓)	(✓)	(✓)	(✓)

Serious Adverse Event Narrative Form (if applicable)		(✓)	(✓)	(✓)	(✓)	(✓)	(✓)
Protocol Deviation Form (if applicable)	(✓)	(✓)	(✓)	(✓)	(✓)	(✓)	(✓)
Interim Masking Decision Form (if applicable) ^f		(✓)	(✓)	(✓)			(✓)

^aTreatment failure can be declared at any visit, including an unscheduled visit.

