5.3.1 USE OF CONTRACEPTION

A woman of childbearing potential (WOCBP) is defined by the Clinical Trials Facilitation Group as “fertile, following menarche and until becoming post-menopausal unless permanently sterile.” Any woman who meets this definition must use highly effective contraception for the timeframe described in Section 5.3.

Highly effective contraception methods as defined by the Clinical Trials Facilitation Group, include:

- Combined (estrogen and progestogen containing) hormonal contraception associated with inhibition of ovulation; oral, intravaginal, or transdermal
- Progestogen-only hormonal contraception associated with inhibition of ovulation; oral, injectable, or implantable
- Intrauterine device (IUD)
- Intrauterine hormone-releasing system (IUS)
- Bilateral tubal occlusion
- Vasectomized partner
- Abstinence from heterosexual intercourse

If abstinence is the selected contraception method, the reliability of this method needs to be evaluated in relation to the preferred and usual lifestyle of the patient.

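### Footnote g to inclusion criterion 5.1 accepts barrier contraception, which Section 5.3.1 does not list as highly effective, and criterion 5.1 omits the 5 post-trial months that Section 5.3 requires

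*Protocol*

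**What the plan says.** The Protocol deals with contraception in four places.

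- **Section 5.1, inclusion criterion.** Participants agree to highly effective contraception for at least "28 days prior to screening and throughout study period (for males and females of reproductive age"). No post-trial period is mentioned.
- **Section 5.1, footnote g**, attached to the words highly effective contraception. The footnote speaks only of effective contraception, and counts drugs, devices and barrier methods.
- **Section 5.3.** Under the lead-in "During this study, participants must", it requires highly effective contraception from at least 1 month before screening, "throughout study period, and at least 5 months following the trial (for males and females of reproductive potential").
- **Section 5.3.1.** Any woman of childbearing potential "must use highly effective contraception for the timeframe described in Section 5.3". The methods are introduced by "Highly effective contraception methods as defined by the Clinical Trials Facilitation Group, include". Seven follow: combined hormonal, progestogen-only hormonal, intrauterine device, intrauterine hormone-releasing system, bilateral tubal occlusion, vasectomized partner, and abstinence.

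**The concern.** One term has two meanings in the same protocol, and the looser meaning sits on the eligibility check. A site that screens from Section 5.1 and its footnotes could accept a barrier method alone and could leave the post-trial period unmentioned. A site that works from 5.3 and 5.3.1 would do neither.

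The stake is participant safety. Section 8.3.8 requires study treatment to stop at once in pregnancy, and concomitant immunomodulators to stop as well because they may harm the fetus. Patients older than 16 may enroll, and Section 5.5 expects about 77% of patients to be female, so the group concerned is not empty.

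**Working it through.** No power, alpha or event count is involved, and the plan gives no figure to reproduce. The check sets the provisions side by side.

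| | 5.1 with footnote g | 5.3 | 5.3.1 |
|---|---|---|---|
| Who | males and females | males and females | women of childbearing potential |
| Standard | highly effective, glossed in the footnote as effective | highly effective | highly effective |
| Barrier methods | accepted | not addressed | not listed |
| Before screening | at least 28 days | at least 1 month | as 5.3 |
| After the trial | nothing stated | at least 5 months | as 5.3 |

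**Methods.** Take a woman of childbearing potential who uses a barrier method and nothing else. Footnote g counts her method, so she can be passed on criterion 5.1. Section 5.3.1 requires a highly effective method, and hers is not among the seven. The word introducing the list could be read as leaving it open. But the list is presented as an outside body's definition, and nothing in 5.3.1 admits barrier methods.

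**Duration.** The pre-screening periods (28 days and 1 month) are practically the same. After the trial, 5.1 states 0 months and 5.3 at least 5, a difference of 5 − 0 = 5 months. For women, 5.3.1 points expressly to the 5.3 period.

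**Contact after the trial.** Section 1.3 says "Patients are contacted approximately 70 days after their last study visit", and only the adverse event form is completed at that call. I assume a 30-day month and count the 5 months from the participant's last visit:

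- required period: 5 × 30 = 150 days
- scheduled contact ends at about day 70
- remainder with no scheduled contact: 150 − 70 = about 80 days

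Clear wording at entry therefore carries much of the protection in the second half of the period.

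**Males.** Sections 5.1 and 5.3 both cover males. The binding sentence in 5.3.1 names women only, and 5.3 lists no methods. Outside footnote g, no provision says which methods a male participant may rely on.

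**How many.** The documents do not count women of childbearing potential. The nearest figure is the expected female share, 0.77 × 118 = 90.9, or about 91 of the planned sample. That is only a loose ceiling on the planning assumption: not all are post-menarche, abstinence is an accepted method, and enrollment stopped early.

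**The case against.** The strongest reply is that the rules can all be met together. Section 5.3 binds independently of 5.1. The first inclusion criterion already asks for willingness to follow all study procedures, and Section 5.4 treats unwillingness to comply as a screen failure. Criterion 5.1 is silent on the post-trial period and does not permit stopping at Month 12. For women, 5.3.1 settles the duration. All of this stands, and it reduces the duration point to an omission from the entry wording.

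On methods, it can be said that criterion 5.1 itself asks for highly effective contraception and that only 5.3.1 defines the term. That is the better reading, but it does not rescue the footnote, which is attached to that very phrase and tells the screener that barrier methods count.

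Risk is also limited by pregnancy testing at every study visit (Section 8.2), although that ends with the visits. And the Data and Safety Monitoring Committee stopped enrollment on 14 February 2024 (Section 10.1.12.5), so rewording 5.1 changes no future eligibility decision. This is right, and it bears on how much action is needed.

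A reader might infer more than the documents support:

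- *That participants can leave the trial free of the 5-month duty.* Section 5.3 imposes it regardless of 5.1.
- *That participants agreed only to the 5.1 wording.* They agree to consent and assent forms, which are not in the reviewed text and may state the 5 months and the method list.
- *That deviation status under SAP 4.2 becomes unclear.* That section does not name contraception, and contraception stopped after the trial falls after the 12-month endpoint.
- *That 5.3.1 exempts males.* It adds detail for women; 5.1 and 5.3 still cover males, whose methods are simply unspecified.

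**Conclusion.** The inconsistency is real in the current protocol text, and it is small. The method conflict is a direct one: footnote g accepts a class of methods that 5.3.1 does not list, so a woman relying on a barrier method alone can be passed as eligible while breaching a mandatory safety rule. The duration point is an omission of 5 months from criterion 5.1, with the duty still in force through 5.3 and, for women, 5.3.1.

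The method conclusion rests on reading the 5.3.1 list as the protocol's definition of highly effective. How many participants are affected cannot be derived, and whether any were misinformed depends on consent forms and a manual that were not available. The primary analysis, sample size and error rate are untouched.

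**What to change.** 1. Replace footnote g with a reference to the Section 5.3.1 list.
2. Add the Section 5.3 post-trial period of at least 5 months to criterion 5.1.
3. State the methods accepted for male participants.
4. Check the consent and assent forms. If they gave a shorter period or accepted barrier methods alone, notify participants still in follow-up or within 5 months of leaving. If they already match 5.3 and 5.3.1, no notice is needed.

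The cost is a few lines of protocol wording and a check of the forms, plus a short notice if that check shows it is needed. With enrollment closed, the wording change mainly corrects the record; the check of the forms is the step that could still protect a participant.
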